2.1 Main purpose

Constructing a foot health risk warning model based on wearable sensors

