Inclusion Criteria	Agree to participate in the study, and the legal representative voluntarily signs the informed consent form Children and adolescents aged 6-18 with typical development, regardless of gender

Exclusion criteria	Except for flat feet, there are other congenital deformities of the lower limbs or spine that affect foot posture. In addition to flat feet, there are other muscle, nerve, and bone diseases that affect foot posture. The researchers have determined that they are not suitable to participate in this study
Effectiveness analysis	Main efficacy indicators: Motional foot posture improvement (push off phase foot flip angle) Secondary efficacy indicators: Static foot posture improvement (foot posture index FPI-6)
Security analysis	The detection equipment and methods used in this study mainly include harmless optical motion capture, structured light 3D scanning, wearable sensors, and bioelectrical resistance body composition analysis; X-ray, bone age, ultrasound and other imaging tests are all operated by professional technicians, and the collection environment and methods meet safety requirements; The intervention method is non pharmacological therapy, which is harmless to the human body; The data acquisition and analysis process strictly follows privacy protection regulations, and there is no security risks.
statistical analysis	Analysis set: Use the full analysis set for statistical analysis. Full analysis set (FAS): Includes all enrolled subjects who have received at least one non pharmacological intervention and have measurable baseline foot injury. Sample size determination: According to epidemiological surveys, the incidence of foot pain events in children is about 12%, and it is determined based on similar studies. Statistical analysis: SPSS 25.0 statistical analysis software will be used for statistical analysis
follow-up	Feedback on foot pain events; Execution of martial arts training and vertical rhythm training; The efficacy and adverse reactions of martial arts training and vertical rhythm training.
Statistical methods	The method used is independent sample t-test to analyze gait parameters of normal and poor foot postures, and repeated measures ANOVA to analyze gait and foot posture parameters before and after intervention.

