prevent the occurrence of injuries in advance. It is even more difficult to control the risk of foot injuries and rehabilitation processes in large-scale children. Therefore, we used Huawei HUAWEI S-TAG inertial sensors to observe the foot posture characteristics of children with foot injuries in the early stage. In the study, it was found that the static and dynamic foot posture of children are closely related to foot pain, mainly due to the significant difference in the angle of calcaneus valgus and the swing angle of the longitudinal axis of the foot during gait (toe push off phase) between normal children and children with foot pain. Based on the above, this project focuses on the research of neural network models for key rehabilitation nodes in the core content of foot injury risk prediction, WBV intervention process, and exercise intervention process. Inertial sensors are used to observe foot posture data 24/7, and regular features in gait before injury and during rehabilitation process are mined. Neural network algorithms are used to construct algorithm models, and recognition and evaluation models are established for earlier "compensated", "decompensated", and "key rehabilitation node" gaits before injury. Prompt for decompensated gait before injury occurs, thereby achieving early warning and monitoring of the rehabilitation process before injury occurs. The prediction accuracy of this model approaches the real world infinitely as the amount of training data continues to increase.

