3.1 Primary endpoint indicator

If a wearable sensor gait detection is completed for 4 weeks and a foot pain event is reported, gait data collection can be stopped.

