13.1 Sample size determination

This study is divided into three stages: the first stage is a prospective intervention study, and the second and third stages are observational studies. The sample size of the experiment is mainly based on the requirements of the first stage research, calculated using PASS 15.0 software. Compare the differences in dynamic and static foot posture between the intervention group and the observation group for subjects with foot pain after 4 weeks of intervention. Require bilateral testing, with $\alpha=0.05$, $\beta=0.1$, and a confidence (testing efficiency) of $1-\beta=90\%$. The expected difference in effect between the intervention group and the observation group is 0.8, so each group requires 34 people, for a total of 102 people in the three groups. According to the preliminary epidemiological investigation, the incidence of foot pain events in children is about 12%. The planned recruitment sample size is 1000 people, which can collect about 120 cases of foot pain events, meeting the sample size requirements.

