13.2 Definition and selection of analysis set

Use the full analysis set for statistical analysis. Full analysis set (FAS): Includes all enrolled subjects who have received at least one non pharmacological intervention and have measurable baseline foot injury.

13.3 statistical method

Independent sample t-test was used to compare gait parameters between children with foot pain and those without symptoms, while repeated measures ANOVA was used to compare dynamic and static foot posture parameters before and after training intervention.

13.4 Statistical software and general requirements:

- All statistical analyses were conducted using SPSS 25.0 (or higher version).
- Measurement data is described using mean, standard deviation, median, maximum, and minimum values
- Count data is described using frequency and percentage

14. Experimental management

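### The main objective is a warning model, but the stated statistical methods (a t-test and a before/after ANOVA) do not measure how well it predicts foot pain

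*Protocol*

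**What the plan says.** - **Objective.** Section 2.1, in line with the synopsis, states the main purpose as "Constructing a foot health risk warning model based on wearable sensors".
- **How the model is built.** The background, section 1.1, says: "Neural network algorithms are used to construct algorithm models, and recognition and evaluation models are established". It adds: "The prediction accuracy of this model approaches the real world infinitely as the amount of training data continues to increase". It gives no performance measure, alert threshold or validation.
- **Methods.** Section 13.3 names two: "Independent sample t-test was used to compare gait parameters between children with foot pain and those without symptoms", and "repeated measures ANOVA was used to compare dynamic and static foot posture parameters before and after training intervention". The synopsis also names a t-test and a repeated measures ANOVA, but with different t-test groups: "The method used is independent sample t-test to analyze gait parameters of normal and poor foot postures".
- **Endpoint and indicators.** The primary endpoint in section 3.1 reads: "If a wearable sensor gait detection is completed for 4 weeks and a foot pain event is reported, gait data collection can be stopped". The main efficacy indicator in section 8.1 is the change in a push-off foot angle after intervention. Neither is a measure of prediction.
- **Size and analysis set.** Section 13.1 sizes the study for the comparison of intervention and observation groups. The one analysis set, in section 13.2, is limited to children who received an intervention and had a measurable foot injury at baseline.

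**The concern.** A warning model is judged by how well it ranks children by risk, whether its predicted risks match observed rates, and how many alerts are right at the threshold used. A t-test asks whether two group means differ. With close to a thousand children, that answer can be a clear yes while the two distributions overlap almost completely. The ANOVA concerns change under training and does not bear on the warning question.

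A trial that followed section 13.3 could therefore report a gait difference between children with and without pain, and separately a fitted network, with no stated estimate of how well the network warns. The main objective would be met in name, and a reader could mistake a small p-value for evidence that the warning works.

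**Working it through.** **Inputs.** From section 13.1: two-sided alpha 0.05, power 90%, expected effect 0.8, 34 per group, 1000 children, 12% incidence. Section 1.1 cites 10% to 15% from other studies. Assumptions: 0.8 is a standardised difference (no unit is given), there is no dropout (no rate is given), and there is one normally distributed gait marker with equal variances in the two groups.

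**1. The plan's own figures.** The normal approximation gives n = 2(1.960 + 1.282)²/0.8² = 32.8, so 33 per group. The exact noncentral t gives power 0.893 at 33 and 0.902 at 34, so the stated 34 is reproduced, and 3 × 34 = 102. Also 0.12 × 1000 = 120 events, leaving 880 children without pain. The sample size is sound for the intervention comparison; it was not set for the model.

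**2. Smallest significant difference, pain versus no pain.**
- SE of d = √(1/120 + 1/880) = 0.0973.
- d at p = 0.05 is 1.962 × 0.0973 = 0.191.
- AUC = Φ(d/√2) = Φ(0.135) = 0.554, where chance is 0.5.
- Sensitivity at 90% specificity = 1 − Φ(1.2816 − 0.191) = 13.8%.
- PPV = 0.138 × 0.12/(0.138 × 0.12 + 0.10 × 0.88) = 15.8%.

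**3. Difference detected with 90% power.**
- d = (1.962 + 1.282) × 0.0973 = 0.316; an observed difference of that size has p of about 0.001.
- AUC = Φ(0.223) = 0.588.
- Sensitivity at 90% specificity = 1 − Φ(1.2816 − 0.316) = 16.7%.
- PPV = 0.167 × 0.12/(0.167 × 0.12 + 0.10 × 0.88), or about 19%, against a base rate of 12%.

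**4. Other event counts.**

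| Pain / no pain | d at p = 0.05 | AUC | d at 90% power | AUC |
|---|---|---|---|---|
| 102 / 898 | 0.205 | 0.558 | 0.339 | 0.595 |
| 120 / 880 | 0.191 | 0.554 | 0.316 | 0.588 |
| 150 / 850 | 0.174 | 0.549 | 0.287 | 0.580 |

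**5. Larger differences.** At d = 0.8, borrowed from the intervention sample size, AUC is 0.714 and sensitivity at 90% specificity is 31.5%. An AUC of 0.80 needs d of about 1.19.

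**6. What the planned size gives if AUC is reported.** The Hanley-McNeil SE with 120 and 880 children is 0.0288 at AUC 0.60, 0.0279 at 0.70 and 0.0250 at 0.80. The 95% intervals are 0.544 to 0.656, 0.645 to 0.755 and 0.751 to 0.849, that is, about ±0.05 to ±0.06.

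**The case against.** The strongest reply has four parts.

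- **The t-test is not the only analysis the protocol mentions.** This stands. Section 1.1 names neural networks for building the model. But that is a construction method in the background; it is not carried into sections 3, 8 or 13 and has no performance measure attached.
- **Section 13.3 never says that the t-test evaluates the model.** This also stands. A reader might infer that the protocol would accept a significant t-test as proof of the warning model, or that the t-test is a wrong method. The text supports neither: for comparing two means it is a valid test. What is at fault is the mismatch between the main objective and the methods stated.
- **Validation detail can sit in a statistical analysis plan that is not shown.** This is true of the resampling scheme, the threshold and the reporting format. It does not fully answer the point, because section 13.3 states which methods will be used, and none of them addresses the main objective.
- **The AUC figures do not describe a neural network fed with continuous sensor data.** Correct. They neither predict nor bound its performance. A model that combines several markers could do better, but a t-test would not show it.

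A reader might also infer that accuracy will be judged on the training data, or with data split by stride or day, and will therefore be inflated. No section plans that. The sentence in section 1.1 on accuracy and growing training data is background, and section 13 does not rely on it.

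**Conclusion.** The point holds as a mismatch between objective and analysis. The main objective is a prediction model, and the methods in section 13.3 and the synopsis are a comparison of means and a before/after comparison, neither of which measures prediction.

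The arithmetic shows why the t-test cannot stand in: at the planned size it can be significant with an AUC near 0.55, and it has 90% power for a marker that misses about 83% of cases at 90% specificity. This rests on the single-marker, equal-variance assumption, the 12% incidence and no dropout. The conclusion changes little between 102 and 150 events.

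The documents do not support going further, to say that the model has no stated method at all, that the t-test is misused, or that optimistic accuracy is planned. The change is worth making before the analysis; it does not put the 34 per group in doubt.

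**What to change.** In section 13.3, and in the synopsis to match:

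- Make the analysis of the main objective the out-of-sample performance of the warning model in all monitored children. The present analysis set, read literally, leaves out those who never have pain, so this population needs naming.
- Use cross-validation or a hold-out set, split by child so that no child contributes to both fitting and testing.
- Report AUC with a 95% CI, calibration, and sensitivity and PPV at a fixed specificity, at the observed event rate.
- Keep the t-test as descriptive, with the same groups in both places.

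No further children or measurements are needed. The cost is revised wording and some extra analysis work. Reported accuracy may be lower than an in-sample figure would be.

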2.2 Secondary purpose

Exploring the correlation between children's foot health and musculoskeletal development;

3. Study endpoint:

3.1 Primary endpoint indicator

If a wearable sensor gait detection is completed for 4 weeks and a foot pain event is reported, gait data collection can be stopped.

3.2 Secondary endpoint indicators

After the occurrence of foot pain events, a 4-week observation or intervention was conducted under the guidance of researchers, and the evaluation of the improvement of dynamic and static foot posture was ultimately completed.

4. experimental design

4.1 overall design

This clinical study is a prospective intervention study. We plan to recruit 1000 participants aged 6-18. Over the next 4 weeks, sensors were used to collect gait data and record the occurrence of foot pain. Children with foot pain will be enrolled in the observation group, exercise intervention group, or WBV intervention group according to their wishes. After 4 weeks of intervention, analyze and compare the differences in dynamic and static foot posture between the intervention group and the observation group. In the second stage, 120 participants aged 8-10 were selected for an observational study on the correlation between foot development and bone age development, and all levels were completed on the day of the study. In the third stage, 30 participants aged 8-10 years were selected for an observational study of gait dynamics using optical motion capture. Complete all levels of the day.

4.2 Randomization and blinding

4.2.1 randomization

In the first stage of this study, it is expected that about 12% of the children will experience foot pain, and eligible/ineligible patients will be enrolled according to their willingness to join the observation group, WBV intervention group, or gongfa intervention group, with at least 34 cases in each group, and no randomization will be conducted.

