4.2.2 Blind state/Breaking blindness

This study will not be conducted in a blinded manner.

5. Subject population

The subjects of this study are children and adolescents aged 6-18 years old.

5.1 Diagnostic criteria: Foot pain diagnosis is based on facial VAS score, foot posture evaluation is based on foot posture index, foot 3D scanning and weight-bearing position foot X-ray, plantar soft tissue development evaluation is based on plantar ultrasound, bone growth and development evaluation is based on left wrist bone age, gene analysis uses saliva samples, traditional Chinese medicine syndrome analysis uses the Four Diagnostic and Traditional Chinese Medicine Tongue Image Intelligent Analysis System, gait and training motion dynamics analysis uses optical motion capture combined with virtual simulation technology, etc.

5.2 Inclusion criteria:

- 1) Agree to participate in the study, and the legal representative voluntarily signs the informed consent form
- 2) Children and adolescents aged 6-18 with typical development, regardless of gender

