7.2 Phase One

We plan to recruit 1000 participants aged 6-18 to record their basic health status and static foot posture at baseline. Subsequently, sensors were used to collect gait data for more than 8 hours per day for the next 4 weeks, and all enrolled children wore wearable sensors in their daily lives. The obtained data is uploaded to the cloud server through a mobile application, and remote monitoring and daily event recording are achieved by uploading the data through the APP. When subjects experience foot pain events, they should promptly report to the researchers through the APP. After determining foot pain based on VAS scores, the subjects with foot pain will be enrolled in the observation group, exercise intervention group, and WBV intervention group according to their wishes. Children in the observation group should rest according to medical advice and not participate in sports activities. Children in the intervention group received WBV vertical rhythm or exercise training programs under the guidance of researchers' follow-up. The follow-up time is once a week, and the training lasts for a total of 4 weeks. Using a self-developed app for researchers to remotely monitor and guide children's training movements, and track training progress.

The device uses Huawei S-TAG foot rings, matched with HarmonyOS 2+/Android 6.0+/iOS 9.0+systems; IP68 (GB/T 4208-2017), waterproof rating of 50 meters; Bluetooth: BT 5.0 transmits data; Running Scene

Battery life: Run for 1 hour per day, run 5 days a week, leave it still when not in use, and have a battery life of 30 days.

(1) WBV Vertical Rhythm Training Standard Process: Children enrolled in the study will be trained at home using vertical rhythm equipment under the guidance of researchers and parental supervision. WBV training lasts for 4 weeks, five days a week, with 15 minutes of training per day. Each movement lasts for 30 seconds, and there is a 30 second break between groups.

(2) Standard process for traditional Chinese medicine exercise training: Children enrolled in the group will undergo exercise training under the supervision of their parents, following the teaching of a self-developed APP. The Yi Jin Jing training will last for 4 weeks, five days a week, with 15 minutes of training per day. There will be a total of 12 exercises, each lasting 1 minute, with a 15 second break between groups.

Figure 2 S-TAG Wearable Sensor

7.3 Phase 2

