8.1 Main efficacy indicators

Dynamic Foot Posture: Gait Push Off Period Foot Outward Angle

Capture the angle of foot valgus during gait push off period through wearable devices, and compare the difference between the values after intervention and before intervention.

[figure not shown]

Figure 8 Schematic diagram of wearable sensor dynamic foot axis

The red dashed line represents the longitudinal axis of the foot, and through wearable sensors, the angle of this axis relative to the reference axis during the stance phase of gait can be calculated.

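### Groups are self-chosen and unblinded, and the efficacy wording (before/after) and the analysis set do not match the intervention-versus-observation comparison on which the design and sample size rest.

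*Protocol*

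**What the plan says.** **Allocation.** A child enters the intervention part once pain is reported and confirmed (7.2): "After determining foot pain based on VAS scores, the subjects with foot pain will be enrolled in the observation group" or one of the two training groups. The child or family makes the choice. Section 4.1 says "Children with foot pain will be enrolled in the observation group, exercise intervention group, or WBV intervention group according to their wishes", 7.2 repeats this, and 4.2.1 says "eligible/ineligible patients will be enrolled according to their willingness to join the observation group, WBV intervention group, or gongfa intervention group". Section 4.2.1 adds that "no randomization will be conducted", and 4.2.2 states "This study will not be conducted in a blinded manner".

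**Comparison the design rests on.** The summary, 4.1 and 13.1 all describe comparing trained children with the observation group after 4 weeks. Section 13.1 sizes the trial for that contrast: two-sided alpha 0.05, power 90%, expected difference 0.8, 34 per group, 102 in all.

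**Efficacy result as worded.** For the push-off foot angle, 8.1 says to "compare the difference between the values after intervention and before intervention". The only efficacy method named is in 13.3: "repeated measures ANOVA was used to compare dynamic and static foot posture parameters before and after training intervention". It mentions no group term, no interaction and no observation group.

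**Analysis set.** Section 13.2 has one set, the FAS. It admits only enrolled children who were given one or more non-drug interventions. Section 7.2 has the observation group rest and stay out of sport.

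**The concern.** Children enter this part because they have just become symptomatic. Section 1.1 reports that push-off angles differed between normal children and children with foot pain in the team's earlier work. It is therefore plausible that the angle moves as pain settles, with or without training. A before/after test in trained children cannot tell the two apart. An observation group can, but only if it is in the analysis set and the comparison with it is the stated efficacy result.

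A second problem remains even then. Pain severity, age and interest in exercise may influence both which group a child picks and how the angle develops over 4 weeks. Subtracting the observation group does not remove that. Together, the two problems could lead to a training benefit being reported where none exists.

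**Working it through.** **1. The plan's own figure.** Inputs from 13.1: difference 0.8 (no unit is given; taken here as SD units), two-sided alpha 0.05, power 0.90.
- Normal approximation: n = 2 × (1.960 + 1.282)² / 0.8² = 32.8, so 33 per group.
- Two-sample t-test: n = 33.83, so 34 per group. Power is 90.15% at 34 and 89.3% at 33.
- 3 × 34 = 102, and 12% of 1000 = 120.

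The 34 reproduces as a two-sample, between-group calculation.

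**2. The sections side by side.**

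| Section | What is compared |
|---|---|
| Summary, 4.1, 13.1 | intervention group against observation group |
| 8.1 | after against before |
| 13.3 | before against after training |
| 13.2 | set limited to children given an intervention |

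The first row and the other three do not describe the same analysis.

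**3. If 8.1 and 13.3 are followed as written.** Assume no training effect, 34 children in one trained group, and a natural mean change of m, in SD of the change. The paired t statistic has noncentrality m√34 on 33 degrees of freedom.

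| m (assumed) | m√34 | False-positive rate |
|---|---|---|
| 0.2 | 1.17 | 20% |
| 0.3 | 1.75 | 40% |
| 0.5 | 2.92 | 81% |

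For the time effect of a three-group repeated measures ANOVA (34 per group, simulated), the rate is 85% at m = 0.3 and above 99% at m = 0.5.

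**4. If the group-by-time contrast is used.** With the same natural change in all three groups, the simulated false-positive rate is 5%. Shared recovery cancels.

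**5. What does not cancel.** Suppose self-selection shifts the change in one group by b, in SD of the change. The two-group test has noncentrality b√(34/2) = b√17 on 66 degrees of freedom. For b = 0.1, 0.2, 0.3 and 0.5 (assumed), the false-positive rate is 7%, 13%, 23% and 53%.

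**6. Does adjusting for the baseline angle solve it?** Let the groups differ by d SD at baseline, let r be the pre/post correlation, and assume equal SD at both times and no true effect.
- *The difference regresses to a common mean.* The expected post difference is rd. The change score is off by d − rd = d(1−r) in size, and baseline adjustment is unbiased. With SD of the change √(2(1−r)), d = 0.3, 0.5 and 0.8 give change-score false-positive rates of 9%, 17% and 37% at r = 0.5, and 8%, 12% and 24% at r = 0.7.
- *The difference is stable.* The expected post difference is d. The change score is unbiased and holds 5%. The baseline-adjusted estimate is off by d − rd = d(1−r). By simulation at r = 0.5, its false-positive rate is about 11%, 20% and 41%.

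The protocol gives none of m, b, d or r.

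**The case against.** The strongest reply is that the protocol does plan a concurrent observation group, names the comparison with it in several places, and sizes the trial for it. Repeated measures ANOVA in three groups can carry that comparison as group-by-time. This stands. A reader might infer from 8.1 and 13.3 that nothing in the plan separates training from natural recovery; 4.1 and 13.1 do not support so strong a reading. What remains is a conflict between sections, and the before/after error arises only if 8.1 and 13.3 are taken literally or the observation group drops out of the FAS.

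The FAS point also depends on a literal reading. Advised rest could be argued to be a non-drug intervention, but 3.2 speaks of observation or intervention as alternatives, so the wording needs settling.

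It is fair, too, that the absence of randomisation is openly declared, and that the main objective (2.1) is the warning model, with the intervention results listed under secondary endpoints (3.2). Model terms and covariates may properly sit in a statistical analysis plan that is not shown, so their absence is not the finding. No such plan would by itself remove the conflict inside the protocol.

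Finally, a reader might assume that baseline adjustment repairs the self-selection. Step 6 shows that it can introduce the same error that it is meant to remove.

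**Conclusion.** The point holds as a conflict between sections plus a limit on what can be concluded. The design and the 34 per group rest on intervention versus observation. Sections 8.1 and 13.3 word efficacy as before/after, and 13.2 read literally removes the comparator. Followed as written, and with no true effect, an assumed natural change between 0.2 and 0.5 SD of the change takes the error rate in one trained group from a nominal 5% to between about 20% and 81%.

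Using the observation group brings the error from shared recovery back to 5%. Bias from the choice of group remains, and its size is unknown: 7% to 53% false positives over the assumed shifts in step 5. It would go too far to say that the trial cannot compare the groups at all. It can, provided that the result is presented as an association. The words eligible/ineligible in 4.2.1 are a minor side point, possibly a translation slip, and carry no weight in the confounding argument.

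**What to change.** 1. In 8.1 and 13.3, make the efficacy result the difference between each training group and the observation group in the pre-to-post change of the push-off angle (group-by-time). Call within-group change descriptive.
2. In 13.2, define the FAS so that observation-group children are included.
3. Add an analysis adjusted for data already planned: VAS at allocation, age, sex, baseline FPI-6, and the sensor angle from before the pain where the child has one. Report the change-score and the baseline-angle-adjusted estimates side by side, because in self-selected groups either can be off by about d(1−r), depending on whether the baseline difference is stable or regresses to a common mean.
4. Word the conclusion as an association, because the groups are self-chosen and unblinded.
5. Reconcile the eligibility wording in 4.2.1 with 5.2, 5.3 and 7.1.

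The cost is protocol wording and a little more analysis, with no added children or visits. The downside is a more modest efficacy claim.
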